18.1.4. Pregnancy outcomes questionnaire (as applicable)

- Self-reported pregnancy outcome:
 - Spontaneous abortion (miscarriage) (≤ 20 gestational weeks)
 - Elective or therapeutic termination
 - Live birth
 - Stillbirth (>20 gestational weeks, prior to delivery)
 - Ectopic pregnancy (a pregnancy outside the uterus)
 - Molar pregnancy (a non-viable fertilized egg implants in the uterus)
- Date of pregnancy outcome
- Gestational age at pregnancy outcome (weeks)

18.1.5. Treating HCP questionnaire for medically attended safety events of interest

The treating HCP will be provided with details of the event as reported by the participant (type of event [e.g. general practitioner visit or hospital admission], reported dates, diagnosis, and outcome) and asked to confirm:

- Whether they were the treating physician for the patient at the reported practice/hospital (if not, details of treating physician to be provided if possible)
- Confirmation of relevant dates (e.g. date of visit/hospitalization, date of discharge)
- Confirmation of the diagnosis (i.e. whether the participant reported diagnosis was correct, or if a different diagnosis was given. If a different diagnosis, details to be provided by the HCP)

- Confirmation of outcome:
 - Recovered/resolved
 - Resolved with sequelae
 - Recovering/resolving
 - Not recovered/not resolved
 - Unknown
- Confirmation of any indication the patient should be considered to be ‘frail’

In addition, if the participant has laboratory confirmed severe COVID-19 disease, the HCP will be asked to assess the possibility of vaccine-associated enhanced disease (VAED) according to published Brighton Collaboration criteria.

19. ANNEX 4. SAFETY EVENTS FOR WHICH A SELF-CONTROLLED RISK INTERVAL (SCRI) ANALYSIS WOULD BE A VALID APPROACH

The following table lists the medically attended safety events of interest for which the Self-Controlled Risk Interval (SCRI) analysis would be a valid approach based on a known risk interval of these events after vaccination. The specific risk windows for each safety event of interest to be included in the SCRI analysis will be detailed in the statistical analysis plan (SAP), and these will be aligned with risk windows informed by the Brighton Collaboration and other published literature as available.

Body System	Safety Event
Neurologic	Generalized convulsion/ seizure
	Guillain-Barré Syndrome (GBS)
	Aseptic meningitis
	Encephalitis / Encephalomyelitis
	Other acute demyelinating diseases
	Transverse myelitis
	Multiple sclerosis
	Optic neuritis
	Bell's palsy
	Acute disseminated encephalomyelitis
Immunologic	Anaphylaxis
	Arthritis and arthralgia
	Multisystem inflammatory syndrome in adults (MIS-A)
	Kawasaki disease
COVID-19	Severe COVID-19 disease
	Deep vein thrombosis
	Pulmonary embolus
	Cerebrovascular stroke
	Acute kidney injury
	Acute liver injury
	Rhabdomyolysis
Cardiac	Myocarditis
	Pericarditis
	Acute myocardial infarction
Hematologic	Thrombocytopenia
	Disseminated intravascular coagulation
Other	Death
	Narcolepsy and cataplexy
	Non-anaphylactic allergic reactions

090177e1991e3913\Approved\Approved On: 18-Jan-2022 22:29 (GMT)

Document Approval Record

Document Name: C4591010_PROTOCOL AMENDMENT 2_07JAN2022

Document Title: C4591010_PROTOCOL AMENDMENT 2_07JAN2022

Signed By:	Date(GMT)	Signing Capacity
[name]	18-Jan-2022 22:26:14	Manager Approval
[name]	18-Jan-2022 22:28:59	EUQPPV Approval

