9.3. Variables

The key vaccine exposure, baseline, and safety outcome variables are listed in Table 1. Detailed definitions are provided in [Section 9.3.1](#).

Table 1. Key vaccine exposure, baseline, and safety outcome variables to be collected in this study

Variable	Role	Data Source(s) ^a
Date of index date dose COVID-19 vaccination	Exposure	Participant and/or their designee
Location where index date dose COVID-19 vaccine was administered	Exposure	Participant and/or their designee
Vaccine lot number (index date dose)	Exposure	Participant and/or their designee
Anatomical site where index date dose COVID-19 vaccine was administered	Exposure	Participant and/or their designee
Date of all subsequent dose(s) COVID-19 vaccination(s)	Exposure	Participant and/or their designee
Location where all subsequent COVID-19 vaccine dose(s) was/were administered	Exposure	Participant and/or their designee
Vaccine lot number (all subsequent doses)	Exposure	Participant and/or their designee

090177e1991e3913Approved\Approved On: 18-Jan-2022 22:29 (GMT)

Table 1. Key vaccine exposure, baseline, and safety outcome variables to be collected in this study

Variable	Role	Data Source(s)^a
Anatomical site where all subsequent COVID-19 vaccine(s) was/were administered	Exposure	Participant and/or their designee
Demographics	Baseline characteristics	Participant and/or their designee
Medical History	Baseline characteristics	Participant and/or their designee
Employment characteristics	Baseline characteristics	Participant
Concomitant medications and other vaccines	Baseline characteristics	Participant and/or their designee
Participant reported safety event of interest (described in Section 9.3.1)	Outcome	Participant and/or their designee
Validated safety event of interest	Outcome	Health care provider (HCP) questionnaire or medical record review
Participant reported hospitalization (date and length of admission)	Outcome	Participant and/or their designee
Validated hospitalization (date and length of admission)	Outcome	Health care provider questionnaire or medical record review
Participant's designee reported death (date)	Outcome	Participant's designee
Validated death (date)	Outcome	Health care provider questionnaire or medical record review
Pregnancy status and last menstrual period (LMP) (if applicable)	Baseline characteristics	Participant, their designee, or medical record review

090177e1991e3913\Approved\Approved On: 18-Jan-2022 22:29 (GMT)

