Expected background rates of safety event of interest will be obtained from the EMA-funded COVID-19 vaccine monitoring ACCESS program (8). The ACCESS program is generating background incidence rates of AESI for COVID-19 vaccines over the period 2017 to 2020 from 10 healthcare databases in 7 European countries (8). The analysis in this study will include age-categories in line with the published incidence rates from ACCESS (18-29; 30-39; 40-49; 50-59; 60-69; 70-79; 80+). For safety event of interest which are not expected to be investigated through the ACCESS program, expected rates will be obtained from historical or concurrent rates reported in the literature, including from reports or data available through health authorities or large databases where possible (9, 10). This OE analysis has been favorably compared with other methods for active surveillance of vaccine safety (10).

For selected endpoints, such as those with acute onset and a defined risk window (listed in Annex 4), a SCRI analysis will be implemented if case counts are sufficient. SCRI analysis, described by Farrington (11, 12, 13), compares incidence rates between “risk” and “control” time periods (intervals) among vaccinated individuals, under the assumption that the risk of onset of a safety event of interest on a day during the risk period is the same as that on a day during the control period. The risk interval is a biologically plausible window of time following a vaccine when a safety event of interest could be caused by the vaccine (Figure 3).

Figure 3. Self-Controlled Risk Interval (SCRI) analysis: defining risk and control intervals

090177e1991e3913\Approved\Approved On: 18-Jan-2022 22:29 (GMT)

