Medically attended safety events of interest caused by the vaccine would be expected to cluster shortly after vaccination, and therefore medically attended safety events of interest caused by the vaccine would be expected to have higher incidence rates in the risk interval than in the control interval for an individual. If medically attended safety events of interest are found to cluster in the pre-defined risk window shortly after vaccination, this would suggest – though not confirm – a causal association. The comparison of the risk to the control windows can be expressed as the ratio of the safety event of interest incidence rate on the risk interval over the 1 on control interval: an incidence rate ratio (IRR) of 1 means that the incidence rate is the same in both intervals, whereas an IRR greater than 1 signals an excess of risk in the risk interval (shortly after vaccination). If the lower limit of the 95% CI of the IRR is greater than 1, the incidence rate in the risk interval is considered significantly higher than that in the control interval; if the upper limit of the 95%CI of the IRR is lower than 1, the incidence rate in the risk interval is considered significantly lower than that in the control interval; if the 95%CI contains 1, the incidence rates are not considered significantly different between the 2 intervals. This methodology has been widely used in vaccine safety studies and has been shown to be a powerful and practical method of assessing vaccine safety, with the self-controlled design implicitly controlling for fixed (non time-varying) confounding factors (e.g. sex, ethnicity) (13, 14).

The SCRI analysis will be carried out as part of the final analysis following database lock. Risk intervals for each safety event of interest will be sourced from published literature. The IRR of medically attended safety events of interest occurring in the risk interval versus the control period will be estimated by fitting a conditional Poisson regression model (15). For each safety event of interest, analyses will be restricted to individuals who experience that safety event of interest either during the risk or the control interval. Sensitivity analysis may be conducted considering different assumptions of the risk and control window lengths.

Table 5 depicts the planned analyses related to each study objective.

Table 5. Planned analysis by study objective

Objective	Outcome of interest	Planned analysis

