18.1.2. Each subsequent COVID-19 vaccine dose questionnaire

- Vaccination information:
 - Manufacturer
 - Date of vaccination
- Pregnancy status (female participants of childbearing potential only)

⁶ https://www.bgs.org.uk/sites/default/files/content/resources/files/2018-05-23/fff_full.pdf

- Any changes in contact information
- Any changes in preferred participant follow-up method

The following additional fields completed if the vaccine received is the Pfizer-BioNTech COVID-19 mRNA vaccine:

- Additional vaccination information:
 - Location (i.e. vaccination center)
 - Vaccine lot number
 - Anatomical site where vaccine was administered
- Any changes in prior submitted medical history
 - Any concomitant medication taken within 7 days prior to vaccination (*Drugbank coded*)
 - Any other vaccinations (other than the COVID-19 vaccine, and other than any previously reported) in the last 6 months
 - Presence of potential active viral disease within previous 3 days prior to vaccination (e.g. fever, symptoms of cold, flu, or other inflammatory/infectious process)

18.1.3. Safety outcome follow-up questionnaire (weekly, monthly, and long-term follow-up, through 24 months following the index date vaccine dose)

In addition to discontinuation data being collected during follow up (discontinuation date, number of vaccine doses received by discontinuation, and discontinuation reason), outcome follow up will include:

- Pregnancy status (female participants of childbearing potential only)
- Have you received any non-routine (unplanned) medical care since your vaccination / last follow-up questionnaire? (*with the below options to be tailored for each country*)
 - Yes – primary care physician / general practitioner
 - Yes – emergency department
 - Yes – hospital (inpatient)
 - Yes – hospital (outpatient)
 - Yes – Intensive Care Unit or High Dependency Unit
 - No

If a participant selects yes to any of the above, they will be asked how many events they need to report, and asked to complete all of the following questions for each event:

- What was the main purpose of your non-routine (unplanned) medical care?
 - I have been diagnosed with this condition in the past, but my symptoms changed or got worse
 - I experienced new symptoms and was diagnosed with this condition for the first time
- Relevant details will be collected:
 - Date of visit
 - Date of end of visit (if applicable)

- Details of HCP (as minimum: name, location, email)

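### The SCRI is framed on day of onset, but no listed form field records it, and Annex 4 calls the method valid for severe COVID-19 and death, where its assumptions are in doubt

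*Protocol*

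**What the plan says.** Section 9.7 compares risk and control intervals within vaccinated people, "under the assumption that the risk of onset of a safety event of interest on a day during the risk period is the same" as on a day in the control period. The rate ratio is "estimated by fitting a conditional Poisson regression model". The only SCRI sensitivity analysis named there varies the window lengths.

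The dates that would feed this analysis are these:

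- Participant form (18.1.3): date of visit and "Date of end of visit (if applicable"). The nearest item to onset is a tick-box, "I experienced new symptoms and was diagnosed with this condition for the first time", which carries no date.
- HCP form (18.1.5): "Confirmation of relevant dates (e.g. date of visit/hospitalization, date of discharge").
- Table 1 (Section 9.3): "Validated hospitalization (date and length of admission") and "Validated death (date"). It has no onset variable.
- Section 11: onset dates are mentioned only for the safety report form, where month and year may suffice. Direct review of the medical record is optional and names no onset item.

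Annex 4 lists events for which the SCRI "would be a valid approach based on a known risk interval of these events after vaccination". Severe COVID-19 and death are on the list. Window lengths are left to the SAP.

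**The concern.** An SCRI assigns each case to a window by its event date. If the date is that of the visit, an onset late in the risk window can be counted in the control window, and an onset before vaccination can be counted in the risk window. Both movements shrink a real excess, which in a safety study is the unwelcome direction. The SAP can choose windows, but it cannot recover a date that was never collected.

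Annex 4 justifies the method by a known risk interval. That is not enough, because the method also needs equal baseline risk in the two windows and the chance to observe the event in both. For severe COVID-19 the vaccine itself changes the baseline risk as protection develops. For death, a person has to survive to enrolment, up to 5 days after the dose, to be in the study at all.

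**Working it through.** The protocol states no SCRI case count, delay or rate ratio, so there is no figure to reproduce. All delays, windows, rate ratios and protection levels below are assumptions. Only the 5-day enrolment limit (Section 9.2.1) comes from the protocol.

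**1. Visit date in place of onset date.** Take risk and control windows of equal length W, a true ratio of 3, baseline rate 1 outside the risk window (including before vaccination), and a fixed onset-to-visit delay d.

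- Adjacent windows: observed ratio = [d + 3(W − d)] / [3d + (W − d)].
- Windows separated by a gap of at least d: observed ratio = [d + 3(W − d)] / W, because no risk-window onset reaches the control window.

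| W (days) | d (days) | Adjacent | Separated by ≥ d |
|---|---|---|---|
| 42 | 7 | 112/56 = 2.00 | 112/42 = 2.67 |
| 42 | 14 | 98/70 = 1.40 | 98/42 = 2.33 |
| 28 | 7 | 70/42 = 1.67 | 70/28 = 2.50 |
| 7 | 3 | 15/13 = 1.15 | 15/7 = 2.14 |

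An exponential delay instead of a fixed one gives similar results. With adjacent 42-day windows and a true ratio of 3, mean delays of 1, 3, 7 and 14 days give 2.82, 2.50, 2.00 and 1.48.

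Under the null (true ratio 1) the result stays at 1.00 at every delay, provided visits for pre-vaccination onsets are counted. If they are excluded, adjacent 21-day windows give 0.95 to 0.44 for mean delays of 1 to 30 days.

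**2. Severe COVID-19 with no vaccine harm.** With protection VE in each window, the ratio is (1 − VE in risk window) / (1 − VE in control window). The control window is taken to come later, because Section 9.3.1 collects events only from enrolment onward.

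- 50% then 80%: 0.5/0.2 = 2.5.
- 30% then 70%: 0.7/0.3 = 2.33.
- 0% then 50%: 1.0/0.5 = 2.0.

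If protection is equal in the two windows the ratio is 1, so residual protection from earlier doses makes the distortion smaller.

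**3. Death after the index dose.** If the first k days of a risk window of R days cannot yield an observed death, the null ratio is (R − k)/R.

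- k = 5: 2/7 = 0.29 for R = 7, and 37/42 = 0.88 for R = 42.
- k = 2: 5/7 = 0.71 for R = 7, and 40/42 = 0.95 for R = 42.

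This uses planned, fixed windows. A separate simulation under the null gave 1.00 with planned windows, but an estimate close to 0 when person-time was cut off at death.

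**The case against.** A reader might infer that the forms hold nothing but visit dates. The protocol does not support that. Dates of death and of admission are collected and validated, so the onset-to-visit gap does not arise for death. The HCP item gives its dates only as examples, and the medical record may be obtained. This part of the objection stands. It does not supply a named onset item for the other events, and record review is optional.

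A reader might also infer that SCRI results will be biased across the board. That is not shown. A delay alone leaves a null ratio at 1 if pre-vaccination onsets are counted, and for events that bring people to care at once (anaphylaxis, seizure, infarction and stroke are my assumed examples) the loss is small. The larger losses also need adjacent windows. The readable text does not state that layout, and Figure 3, which defines the intervals, cannot be seen in the copy reviewed.

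For severe COVID-19, a ratio as high as 10 needs 0% protection in the risk window and 90% in the control window. That does not describe people enrolling at a second or booster dose, whom this version of the protocol admits. Nor does the protocol support the claim that a raised ratio would be read as vaccine-enhanced disease. Enhanced disease is assessed separately by case definition and by the HCP, and Section 9.7 says that clustering would suggest causation without confirming it.

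Finally, the SCRI is a secondary analysis, done as feasible and only with enough cases, and Section 9.5 calls the secondary analyses exploratory. This limits the stakes. For death, the start of the risk interval could be settled in the SAP. Annex 4 nevertheless already declares the method valid for it without qualification.

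**Conclusion.** The point holds in a bounded form. The analysis is framed on onset, no listed participant or HCP field records onset, and the named sensitivity analysis does not touch event dating. True ratios may therefore be attenuated for events where care lags onset. How far depends on the delay and the window layout, neither of which the protocol gives.

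For severe COVID-19 the equal-risk assumption is doubtful by design. The direction is towards a false excess, and its size rests wholly on assumed protection levels. For death the bias is downward and is confined to the index dose, because participants receiving later doses are already enrolled. It is largest for short windows and late enrolment, and a 5-day gap is the extreme case.

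The primary incidence rates are not affected. This should be corrected, and earlier is better, because each reported event without an onset date adds to the later query load.

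**What to change.** 1. Add a date-of-first-symptom field to the event block of 18.1.3 and to the HCP form in 18.1.5. Use it to assign cases to SCRI windows, with visit date as the fallback when onset is unknown. Repeat the analysis on visit date as a sensitivity analysis.
2. Limit this to the SCRI. Do not re-date events for the incidence rates or the observed-to-expected comparison. The outcome there is a medically attended event, and the background rates come from healthcare databases, presumably dated by recorded care. Moving only the observed side could create a mismatch.
3. Delete severe COVID-19 from Annex 4. Keep it in the incidence rates and in the enhanced-disease description.
4. Delete death from Annex 4, or start its index-dose risk interval at enrolment. If it is kept, state that planned windows are used and are not cut off at death.

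The cost is one date field on two existing forms and one or two edits to Annex 4. The main downside is that events already reported need a retrospective query for onset date.
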